## **10.2. Dose-Adjustments and Delays of CB-839**

Given the limited number of patients treated to date and the open label, nonrandomized nature of the studies to date, the safety profile of CB-839 has not been fully established. An overall summary of the available safety and tolerability data was profiled above in section 2.4.2.

Overall, CB-839 has been well tolerated across all dose levels tested to date. The large majority of toxicities that have been observed to date have been Grades 1 and 2 and manageable with supportive care and/or interruption of study drug.

Careful application of the dose-escalating rules and close observation of the subjects should minimize the potential risk of dosing with CB-839.

Based on available data, adverse events that are most likely to be observed with CB-839 treatment are mild to moderate and include fatigue, gastrointestinal events (nausea, vomiting, anorexia), photophobia and elevated liver function tests.

Photophobia and related ocular toxicities (e.g., photopsia) have been identified as CB-839-related events. In almost all cases, these events have been Grade 1 and generally do not have an impact on the patient's daily life, although one Grade 2 event required the patient rest for 1-2 hr in a dark room. These events appear to occur around Cmax (1-4 hr after dosing) and resolve with time. Anecdotal reports suggest that tachyphylaxis develops and these events tend to become less frequent over extended dosing. More severe cases can be managed with dose reduction and the use of sunglasses may be considered.

The study personnel must be able to recognize and diagnose these potential adverse events and initiate prompt intervention. In particular, regular monitoring of liver function tests and renal function is recommended.

**Upon withholding CB-839 for adverse event, CB-839 may be restarted when the associated adverse event has returned to  $\leq$  Grade 1, or to the patient's baseline value. (The baseline value is defined as the most immediately known value in place prior to patient's first receipt of CB-839 on Cycle 1, Day 1.)**

**For adverse events deemed by the investigator to be clinically significant and as possibly, probably, or definitely related to CB-839 treatment:**

- **Grade 1 or 2:** Manage with appropriate supportive care.
- **Grade 3 or 4:** Hold CB-839 and Dose Reduce (by 1 or more dose levels) upon resumption

Note the CB-839 dose levels are indicated in Section 8.1. Accordingly, **a patient unable to tolerate CB-839 at a minimum dose of 400mg BID would be unable to continue the study.**

In the event of any *unrelated* adverse events, the investigator may choose to interrupt CB-839 for up to 28 days, but no dose reduction should occur.

**CB-839 treatment may be delayed for up to 4 weeks from the last dose.** If CB-839 is interrupted for more than 28 days, written permission to continue CB-839 must be obtained from the sponsor-investigator subsequent to consultation with the investigator.

If CB-839 is held for toxicity, tolerated treatment with panitumumab and/or irinotecan should continue as scheduled until CB-839 is permanently discontinued – at which time the patient must also permanently discontinue the study (per Section 8.6: a patient must permanently discontinue the study if unable to tolerate CB-839; within the study, a patient will not receive panitumumab + irinotecan as an exclusive 'double-agent' therapy.)

### **10.3. Dose-Adjustments and Delays of Panitumumab**

Throughout the study, panitumumab is scheduled to be administered every two weeks (i.e. on Days 1 and 15 of each 28-day cycle).

Panitumumab dose withholding, reduction, or re-escalation (see Section 10.3.3 and Figure 3) following a previous dose-reduction may be required for patients who experience adverse events felt by the investigator to be at least possibly related to panitumumab.

As needed for management of potential panitumumab-related toxicity, the dose reduction levels for panitumumab are listed in Table 3 below:

**TABLE 4: Panitumumab Dose Reduction Levels**

	Starting Dose	Dose Reduction Level -1	Dose Reduction Level -2
Percentage	100 %	80 %	60 %
Panitumumab Dose	6 mg/kg	4.8 mg/kg	3.6 mg/kg

*(As needed for management of adverse event.)*

### **10.3.1 Criteria for Withholding a Dose of Panitumumab**

Panitumumab will be withheld if any of the following related toxicities occur:

#### Skin-related or nail-related toxicities:

- Symptomatic skin-related or nail-related toxicity requiring narcotics, systemic steroids, or felt to be intolerable by the subject
- Skin or nail infection requiring IV antibiotic or IV antifungal treatment
- Need for surgical debridement
- Any skin-related or nail-related serious adverse event.

#### Non-skin-related or Non-nail-related toxicities:

- Any Grade 3 or 4 toxicity (except alopecia) with the following exceptions:
  - Panitumumab will only be withheld for symptomatic hypomagnesemia and/or hypocalcemia that persists despite aggressive magnesium and/or calcium replacement
  - Panitumumab will only be withheld for Grade 3 or 4 nausea, vomiting, or diarrhea that persists despite maximum supportive care
  - Panitumumab will only be withheld for Grade  $\geq 3$  anemia or Grade 4 thrombocytopenia that cannot be managed by transfusion(s) or cytokine therapy.

### **10.3.2 Criteria for Re-treatment with Panitumumab**

Panitumumab administration may recommence once the reason for withholding the dose of panitumumab has resolved. Panitumumab-related toxicity will be considered "resolved" if it improves to an extent that meets the following criteria for re-treatment with panitumumab:

#### Skin-related or nail-related toxicities:

Panitumumab administration may recommence once:

- The adverse event has improved to  $\leq$  Grade 2 or returned to baseline, and
- The skin-related or nail-related toxicity is no longer intolerable to the subject, and
- Systemic steroids are not required, and
- IV antibiotic or IV antifungal treatment is not required.

#### Non-skin-related or Non-nail-related toxicities:

Panitumumab administration may recommence once the adverse event has improved to  $\leq$  Grade 1 or returned to baseline.

### **10.3.3 Dose Modification Schedule for Panitumumab**

Subjects should be assessed for panitumumab toxicity before each dose.

With the understanding that the patient's study physician may elect a more conservative course of action, subjects who have had their dose of panitumumab withheld for one or more of the reasons listed in Section 10.3.1, and then subsequently meet the criteria for re-treatment as listed in Section 10.3.2, will recommence panitumumab according to the following schedule and as outlined in Figure 3 (note: panitumumab-related toxicity will

be considered “resolved” if it improves to an extent that allows for re-treatment with panitumumab, as per Section 10.3.2):

[figure not shown]
- Subjects receiving either 100% or 80% of the starting dose of panitumumab are allowed to have up to 2 subsequent doses withheld for toxicity. (However, the second dose should only be withheld if the toxicity has not resolved by the time that the subsequent dose is due – for additional context, see the “double-dagger” footnote “‡” in Figure 3.)
- Subjects treated at the 100% dose level whose toxicity resolves after 1 dose of panitumumab is withheld should be re-started at the 100% dose level (recommended but not required). A reduction to the 80% dose is allowed as an alternative to re-challenge with the 100% dose.
- If toxicity recurs, subjects treated at the 100% dose or 80% dose should be re-started at the 80% dose or 60% dose, respectively, when the toxicity resolves after withholding 1 or 2 doses of panitumumab. Subjects treated at the 100% dose level whose toxicity resolves only after 2 subsequent doses of panitumumab are withheld should be re-started at the 80% dose level.
- Subjects treated at the 80% dose level whose toxicity resolves after withholding 1 or 2 doses of panitumumab should be re-started at the 60% dose level.
- Subjects who experience toxicity at the 60% dose level will not be re-treated with panitumumab.

It is recommended that panitumumab doses will be escalated in subjects whose toxicity resolves to the degree that meets the criteria for re-treatment with panitumumab (see Section 10.3.2). Dose escalations are recommended but not required. Dose escalations should occur in the following manner:

- Subjects treated at the 80% dose level whose toxicity does not recur should receive the 100% dose level at the next dose unless a previous attempt to re-escalate to the 100% dose level was not tolerated (re-initiation of the 80% dose is allowed as an alternative to dose escalation).

- Subjects treated at the 60% dose level whose toxicity does not recur should receive the 80% dose at the next dose unless a previous attempt to re-escalate to the 80% dose level was not tolerated (re-initiation of the 60% dose is allowed as an alternative to dose escalation).

**FIGURE 4: Panitumumab Dose Modification Algorithm for Toxicity**

As per Section 12.1, adverse events will be graded according to the NCI's Common Terminology Criteria for Adverse Events (NCI CTCAE), Version 4.03, dated June 14, 2010.

For purpose of managing potential panitumumab-related toxicity, adverse events graded according to CTCAE version 4.03 will be reconciled with guidance presented in Figure 3 according to Table 4:

**TABLE 5: Reconciliation of AE Severity Grades in CTCAE v4.03 versus Figure 3**

CTCAE v4.03 severity grade a	Equivalent to	Figure 3 severity
Grade 0, 1 or 2	=	No / Mild / Moderate
Grade 3	=	Severe
Grade 4	=	Life Threatening or Disabling

(As needed for purpose of managing potential panitumumab-related adverse event.)

a NCI's Common Terminology Criteria for Adverse Events (NCI CTCAE), Version 4.03, dated June 14, 2010.

Dose delays and or modifications for panitumumab are to be considered for skin reactions of Grade 3 that are symptomatic; or which are considered intolerable at any grade.

**Exception for Grade 3 *asymptomatic* rash:** Note that rash of Grade 3 by body surface area (BSA) but which is asymptomatic does not require panitumumab treatment delay (or dose reduction) if uninterrupted panitumumab treatment is medically acceptable per investigator discretion.

Note: If, during the course of managing a patient's panitumumab treatment, conflicting guidance were to be detected between the management guidance as presented by narrative in Section 10.3, versus the algorithm presented in Figure 3, the investigator may elect either course of action deemed most appropriate by the investigator.

If panitumumab is held for toxicity, tolerated treatment with CB-839 + irinotecan may continue as scheduled. Alternatively, if panitumumab is delayed, the investigator may choose to also delay administration of irinotecan.

Delays of panitumumab administration beyond 6 weeks of last administered dose of panitumumab are not allowed. **Subjects who miss 3 or more consecutive scheduled doses of panitumumab due to toxicity or who are unable to receive a dose of panitumumab within 6 weeks of having received their previous dose of panitumumab due to toxicity will be considered unable to tolerate panitumumab and will not be retreated with panitumumab.** Additional consideration may be made toward continuing treatment with CB-839 + irinotecan alone.

#### **10.4. Dose-Adjustments and Delays of Irinotecan**

As needed for management of potential irinotecan-related toxicity, the dose reduction levels for irinotecan are listed in Table 5 below:

**TABLE 6: Irinotecan Dose Reduction Levels**

	Starting Dose	Dose Reduction Level -1	Dose Reduction Level -2
Irinotecan Dose	180 mg/m 	150 mg/m 	120 mg/m 

(As needed for management of adverse event.)

##### **10.4.1 Dose Modification Schedule for Irinotecan**

Throughout the study, irinotecan is scheduled to be administered every two weeks (i.e. on Days 1 and 15 of each 28-day cycle).

Irinotecan should not be administered until:

- Absolute neutrophil count has recovered to  $\geq 1000 /mm^3$ , the
- Platelet count has recovered to  $\geq 100,000 /mm^3$ , and
- Treatment-related diarrhea is fully resolved to (or controlled at) baseline level.

The treating physician may require that a patient return to baseline bowel function without requiring antidiarrheal medication for at least 24 hours before the next chemotherapy administration. (The baseline status is defined as the most immediately known status in place prior to initiation of the patient's first protocol-indicated irinotecan on Cycle 1, Day 1.)

Irinotecan treatment should be delayed 1 or 2 weeks, and if necessary up to 4 weeks, to allow for recovery from irinotecan-related toxicity.

Dose modifications for irinotecan therapy should be carried out according to Table 6 (with the understanding that the patient's study physician may elect a more conservative course of action):

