10. Pharmacokinetic blood samples for research will be collected during each radiotracer injection (F-FSPG and C-Glutamine (if applicable)) in order to perform pharmacokinetic modeling (only for those patients enrolled in the optional Phase I imaging sub-study and all patients enrolled in Phase II). Details regarding PK collection and handling are provided in the lab manual. Pharmacodynamic (PD) blood samples for research to be obtained on Cycle 1, Day 1 (collected once prior to initiating protocol-indicated treatment) for all patients enrolled in Phase II; Pre-Dose on Cycle 1, Day 28 (or alternatively and ideally obtained during Week 4 of Cycle 1, on same-day as F-FSPG PET/CT scan, prior to morning oral dose of CB-839); and at End-of-Treatment.
11. All patients are scheduled to receive panitumumab as a 60 minute (if dose  $\leq$  1000 mg) or 90 minute (if dose  $>$  1000 mg) intravenous infusion on Day 1 and Day 15 of each 28 day cycle. (Note: If an initial 60 minute infusion is tolerated, subsequent panitumumab infusions of  $\leq$  1000 mg may be administered over 30 to 60 minutes.) The site will obtain panitumumab as standard of care from commercial supply.
12. All patients in dose escalation are scheduled to receive irinotecan as a 90-minute intravenous infusion on Day 1 and Day 15 of each 28 day cycle. The site will obtain irinotecan as standard of care from commercial supply. Note: Panitumumab and irinotecan are to be administered as separate infusions. On days when both drugs are administered (i.e. scheduled for Days 1 and 15 of each cycle), the panitumumab infusion will be completed BEFORE initiation of the irinotecan infusion.
13. C-Glutamine PET/CT and F-FSPG PET/CT scan for patients enrolled in optional imaging sub-study for Phase I; F-FSPG PET/CT is required for all patients enrolled to Phase II. Ideally completed on Cycle 1, Day 28, but for purpose of scheduling flexibility: Scans can be completed anytime during Week 4 of Cycle 1 (i.e. during Days 22-28 of Cycle 1), or alternatively as late as prior to administration of any protocol-directed treatment on Day 29 (i.e. prior to initiating intended treatment on Cycle 2, Day 1).
14. Beginning with Cycle 2, Day 15: In order to accommodate scheduling, visits and procedures may occur with flexibility of  $\pm$  1 day.

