If irinotecan is held for toxicity, tolerated treatment with CB-839 + panitumumab may continue as scheduled. Alternatively, if irinotecan is delayed, the investigator may choose to also delay administration of panitumumab.

Subjects who require persistent 1 or 2 week delays for resolution of recurring Grade 1 toxicities, may have their irinotecan dose reduced by 1 dose level to permit administration of irinotecan every 2 weeks, at the investigator's discretion.

If, despite optimal supportive care and a treatment interruption, diarrhea does not resolve to CTC AE Grade ≤ 1 or baseline within 28 days, treatment with irinotecan should be permanently discontinued. However, in the event that the patient is deriving obvious clinical benefit according to the investigator's judgment, further treatment with irinotecan will be decided in agreement between the sponsor-investigator and the investigator. **Otherwise, subjects who require more than 2 dose reductions of irinotecan, or miss 2 or more consecutive scheduled doses due to toxicity, or are unable to receive a dose of irinotecan within 4 weeks of having received their previous dose of irinotecan due to toxicity, will be considered unable to tolerate irinotecan and will not be retreated with irinotecan.** Additional consideration may be made toward continuing treatment with CB-839 + panitumumab alone.

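### Phase I irinotecan: Section 10.4.1 allows toxicity delays of up to 4 weeks past the due date but bars retreatment 4 weeks after the previous dose, and Table 7 footnote d exempts uncontrolled instead of controlled nausea or vomiting

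*Combined protocol and SAP*

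**What the plan says.** Section 10.4.1 states that "irinotecan is scheduled to be administered every two weeks", on Days 1 and 15 of each 28-day cycle. It then gives the recovery allowance: "Irinotecan treatment should be delayed 1 or 2 weeks, and if necessary up to 4 weeks, to allow for recovery from irinotecan-related toxicity". It does not say from when the delay is counted.

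The text after Table 7 closes the same section with a bolded rule. Subjects who need more than two dose reductions, "miss 2 or more consecutive scheduled doses due to toxicity, or are unable to receive a dose of irinotecan within 4 weeks" of their previous dose because of toxicity, count as unable to tolerate irinotecan and are not retreated. That rule opens with the word *Otherwise*. It follows a diarrhea rule (if diarrhea has not recovered "within 28 days, treatment with irinotecan should be permanently discontinued") and an exception: "in the event that the patient is deriving obvious clinical benefit", further irinotecan is settled between the investigator and the sponsor-investigator.

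For panitumumab, also given every 14 days, Section 10.3.3 says "Delays of panitumumab administration beyond 6 weeks of last administered dose of panitumumab are not allowed" and stops treatment in subjects who "miss 3 or more consecutive scheduled doses of panitumumab due to toxicity".

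Table 7 recommends irinotecan dose changes by toxicity grade. For other non-hematologic toxicities, footnote d lists what is left out unless the investigator elects otherwise. The list ends with nausea or vomiting that optimal management has *not* brought under control.

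**The concern.** The two irinotecan limits differ by two weeks. For a Phase I patient who is three or four weeks late because of irinotecan toxicity, with no clinical-benefit agreement, one line permits the next dose and the other ends irinotecan for good. Two clinicians who each follow the text could treat that patient differently. Section 10.3.3 has a tie-break for conflicts between its narrative and its figure. Section 10.4 has none.

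Footnote d decides which toxicities lead to a held and reduced dose of a cytotoxic drug whose listed common reactions include nausea and vomiting. Read literally, the well-managed patient is reduced and the badly affected one is not.

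**Working it through.** The documents give no figure to reproduce here; the check is timeline arithmetic and a comparison of texts.

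**Inputs.** Dosing interval 14 days (Section 10.4.1). Longest permitted delay 4 weeks = 28 days (Section 10.4.1). Retreatment limit 4 weeks = 28 days from the previous dose (bolded rule after Table 7). Irinotecan dose levels 180, 150 and 120 mg/m² (Table 6).

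**Step 1: one clock for both limits.** Days since previous dose = 14 + days past the due date.

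| Delay past due | Days since previous dose | Delay sentence | Bolded 4-week rule |
|---|---|---|---|
| 7 | 14 + 7 = 21 | allowed | allowed |
| 14 | 14 + 14 = 28 | allowed | allowed (at the limit) |
| 15 | 14 + 15 = 29 | allowed | barred |
| 21 | 14 + 21 = 35 | allowed | barred |
| 28 | 14 + 28 = 42 | allowed | barred |

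**Step 2: size of the overlap.** The lines disagree for delays of 15 to 28 days: 28 − 14 = 14 days, and 14 / 28 = 50% of the permitted delay days.

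**Step 3: can the delay be counted from the last dose instead?** With a 14-day interval, a one-week delay so counted would fall before the next dose is due, and a two-week delay would be no delay. The text after Table 7 also uses delays of 1 or 2 weeks for slippage from the two-weekly schedule. Where the protocol counts from the last dose it says so: Section 10.2 for CB-839 and Section 10.3.3 for panitumumab. This reading fails.

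**Step 4: the missed-dose trigger.** With the previous dose on Day 1, the next are due on Days 15 and 29. A delay of more than 14 days normally passes both, so this trigger is generally met too. *Miss* is not defined, however, and a late dose might count as delayed. The conflict rests on the 4-week limit alone.

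**Step 5: the panitumumab comparison.** Six weeks = 42 days = 14 + 28, so the limit for that drug equals a delay of 4 weeks past due. Three missed doses fit the same clock.

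**Step 6: footnote d.** Controlled Grade 2 nausea stays in the table: hold, then one level down, 180 to 150 mg/m², (180 − 150) / 180 = 17%. Uncontrolled Grade 4 vomiting is by default outside the two-level step, 180 to 120 mg/m², (180 − 120) / 180 = 33%. For panitumumab, Section 10.3.1 runs the other way and withholds for Grade 3 or 4 nausea or vomiting that maximum supportive care has not settled. The conditions in Section 10.4.1 that must be met before irinotecan is given cover neutrophils, platelets and diarrhea, so they do not catch vomiting.

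**The case against.** The strongest reply is that the text largely shows which line governs. The delay sentence is general and names no starting point. The later rule is specific, bold and mandatory, and defines its own clock. A more conservative course is always open, so following the stricter line breaches nothing. This stands as a reason to call the defect modest, but the permissive sentence remains in force as written.

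Second, the clinical-benefit agreement may absorb some of the conflict. If *Otherwise* carries it beyond diarrhea, delays past 28 days from the last dose could all go through that agreement. Its scope is unclear, and the words *if necessary* in the delay sentence are not tied to any agreement. This narrows the conflict without removing it.

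Third, Section 10.1 counts inability to start Cycle 2 within 4 weeks of its scheduled date as a DLT, so the protocol elsewhere uses a clock that starts at the due date. This supports leaving the sponsor free to choose the longer limit. It does not reconcile the two irinotecan lines.

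On footnote d, the table is advisory and the investigator may elect otherwise. A related Grade 4 non-hematologic event in Cycle 1 is a DLT and prompts evaluation for a hold or modification. Section 10.2 holds and reduces CB-839 for clinically significant related Grade 3 or 4 events, and Section 8.6 allows discontinuation. The panitumumab rule is only an analogy. These safeguards soften the default, but none supplies the irinotecan dose step that the footnote removes.

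A reader might also infer that the 28-day diarrhea window is wrong. The documents show only that its start is unstated; it is tied to a treatment interruption, and *Otherwise* may set it apart from the bolded rule. Nor should the calendar allowance in Section 6.1, note 14 ("In order to accommodate scheduling, visits and procedures may occur with flexibility of" one day either way) be used to shrink the overlap: it begins with Cycle 2, Day 15, and nothing extends it to the retreatment limit.

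**Conclusion.** Both points hold as defects of wording that should be corrected. Toxicity delays of more than 2 and up to 4 weeks past due (29 to 42 days since the previous dose) are permitted by one line of Section 10.4.1 and barred by another, unless the clinical-benefit agreement applies. Footnote d is reversed.

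The first conclusion assumes that the delay is counted from the due date, the only reading that gives the shorter delays any meaning. The 50% describes permitted delay days. A reader might take it as the share of patients or doses at risk, but the documents do not say how many patients would have such a delay. At most 12 Phase I patients are exposed (Section 8.1).

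A reader might also infer that the dose-escalation result is compromised. The documents do not support that: Section 10.1 sets its own DLT criteria, with a separate clock for starting Cycle 2, and nothing shows that the conflict would alter a DLT call or the MTD. Phase II gives no irinotecan.

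**What to change.** **Delay limit.** Preferred, because it keeps the more cautious bolded rule: reword the delay sentence in Section 10.4.1 along the lines of *irinotecan may be delayed 1 or 2 weeks past the scheduled date (at most 4 weeks from the previous irinotecan dose); beyond this, the discontinuation rule and clinical-benefit provision below apply*. If the sponsor does intend a 4-week delay, keep that sentence and change the bolded rule to 3 missed doses or 6 weeks from the previous dose, as for panitumumab. The documents do not settle which was meant, so the sponsor should state it. Leave the 28-day diarrhea window as it is; at most, state when it starts.

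**Footnote d.** Delete *not* from the clause on nausea and vomiting, so that controlled events are the ones left out.

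**Cost.** Protocol wording only. Under the preferred option, if the delay sentence governs in practice, irinotecan would stop up to 14 days earlier (42 − 28) for patients with longer toxicity delays and no clinical-benefit agreement. Continuing CB-839 with panitumumab may still be considered for them. The alternative would allow retreatment up to 14 days later than the bolded rule now does. The footnote change costs nothing.

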### **9.4. Palliative Radiotherapy**

Radiotherapy other than palliative radiotherapy for symptom control is not allowed concomitantly with the administration of protocol-indicated treatment.

After study enrollment, palliative radiotherapy may be given for bone pain or for other reasons, provided that the total dose delivered is in a palliative range according to institutional standards.

The irradiated area cannot be used for tumor response assessment.

During palliative radiotherapy, study treatment should be delayed and may be resumed once the patient has recovered from any radiation associated toxicity.

If a treatment cycle is interrupted for more than 28 days, the decision to continue will be made by the investigator in agreement with the sponsor-investigator. Continuous interruption of >28 days due to palliative radiotherapy will not be allowed.

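### Section 10.4.1 allows an irinotecan toxicity delay of up to 4 weeks without saying from when; on the reading its wording supports, it conflicts with the stopping rule for doses 15 to 28 days past due (phase I only)

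*Combined protocol and SAP*

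**What the plan says.** Section 10.4.1 fixes the schedule: "Throughout the study, irinotecan is scheduled to be administered every two weeks (i.e. on Days 1 and 15 of each 28-day cycle". It then gives the delay guidance: "Irinotecan treatment should be delayed 1 or 2 weeks, and if necessary up to 4 weeks, to allow for recovery from irinotecan-related toxicity". That sentence does not say whether the weeks run from the date the dose was due or from the last dose given.

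The text after Table 7 contains a stopping rule with three triggers, two of which concern timing. One covers patients who "miss 2 or more consecutive scheduled doses due to toxicity". The other covers patients who "are unable to receive a dose of irinotecan within 4 weeks of having received their previous dose of irinotecan due to toxicity". Either way the patient "will be considered unable to tolerate irinotecan and will not be retreated with irinotecan".

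Just before that rule, the same paragraph stops irinotecan for diarrhea that has not settled within 28 days. It allows further irinotecan by agreement between the investigator and the sponsor-investigator when there is obvious clinical benefit. The stopping rule follows and opens with the word *otherwise*.

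**The concern.** Both statements use the figure of 4 weeks, but they appear to count it from different days. If the delay guidance runs from the due date, its third and fourth weeks lie wholly beyond the point at which the stopping rule has already ended irinotecan. One reader would hold the dose and then re-challenge the slowly recovering patient. Another would record irinotecan intolerance and consider continuing CB-839 plus panitumumab alone.

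The Synopsis and Section 2.5 give collection of toxicity data on the triplet as the reason irinotecan is in phase I. Which sentence the treating team follows determines irinotecan retreatment, cumulative exposure and who is recorded as intolerant. It also determines which course of action would count as a protocol deviation.

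**Working it through.** There is no sample-size or power figure to reproduce; the check is a day count.

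**Inputs, all from Section 10.4.1**
- Dosing interval: 14 days.
- Delay guidance: at most 4 weeks = 28 days, start not stated.
- Stopping rule by time: no dose within 28 days of the previous dose.
- Stopping rule by count: 2 or more consecutive scheduled doses missed.

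**Step 1. Which starting point does the delay guidance use?** Let L be days past the due date and T days since the last dose, so T = 14 + L.
- Counted from the last dose, 1 week gives T = 7, so L = 7 − 14 = −7 (a week early). Two weeks gives T = 14, so L = 0 (on time). Neither is a delay.
- Counted from the due date, 1 and 2 weeks give L = 7 and L = 14, which are delays.

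The text after Table 7 uses the word in the second sense: "Subjects who require persistent 1 or 2 week delays for resolution of recurring Grade 1 toxicities, may have their irinotecan dose reduced by 1 dose". The stated aim there is to restore 2-weekly dosing. Section 10.1, item 3, also counts 4 weeks from scheduled treatment when it defines failure to start Cycle 2 as dose-limiting.

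**Step 2. Limits on a common scale**
- Delay guidance from the due date: L ≤ 28, so T ≤ 14 + 28 = 42.
- Stopping rule by time: T ≤ 28, so L ≤ 28 − 14 = 14.
- Stopping rule by count, if the calendar stays fixed and a delayed dose counts as missed: dosing slots fall at T = 14, 28 and 42, and fewer than 2 may have passed untreated.

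| Days past due (L) | Days since last dose (T) | Delay guidance, from due date | Stop by time | Slots missed | Stop by count |
|---|---|---|---|---|---|
| 7 | 21 | allowed | not met | 1 | not met |
| 14 | 28 | allowed | not met | 1 | not met |
| 15 | 29 | allowed | met | 2 | met |
| 21 | 35 | allowed | met | 2 | met |
| 28 | 42 | allowed | met | 2 | met |
| 29 | 43 | not allowed | met | 3 | met |

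The instructions differ for L = 15 to 28. That is 14 days, half of the 28-day delay period.

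**Step 3. Example.** Last dose on Cycle 1 Day 15; next dose due Day 29. The delay guidance runs to Day 29 + 28 = Day 57. The stopping rule by time runs to Day 15 + 28 = Day 43. For recovery on Days 44 to 57 the two give opposite answers.

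**Step 4. Sensitivity to the starting point.** If the delay guidance is counted from the last dose, its limit is also T ≤ 28 and the conflict disappears, but the 1- and 2-week delays then have no meaning (Step 1).

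**The case against.** The strongest reply is that the due-date reading is inferred. Section 10.2 counts the CB-839 limit (4 weeks) and Section 10.3.3 the panitumumab limit (6 weeks) expressly from the last dose, and a site could carry that convention over to irinotecan. This stands to the extent that a reader should not infer that the protocol expressly writes two starting points; it writes one and leaves the other open. It does not remove the problem, because the convention empties the 1- and 2-week delays of meaning.

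Second, the delay sentence is general guidance and the stopping rule is specific and mandatory, so many readers would let the latter govern. That is reasonable, but the document does not say so, and the third and fourth weeks could then be used only where some exception applies. The clause letting the investigator choose between conflicting instructions, in Section 10.3.3, covers only panitumumab. The discretion in Section 10.4.1 to take a more conservative course does not settle which rule is in force.

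Third, the clinical-benefit agreement may lift the bar for some patients. This stands in part. The agreement is attached to the diarrhea sentence, and *otherwise* leaves it unclear whether it reaches the stopping rule. A reader might infer that every patient 15 to 28 days late is both still on irinotecan and permanently off it; the text does not support that for patients who may fall under the agreement.

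Fourth, the missed-dose trigger is not independent proof of the window. The protocol does not define a missed dose, and Table 7 uses both delaying and omitting a dose. Section 10 keeps visits and assessments on the original timeline during an interruption, but does not say that a delayed irinotecan dose counts as missed. The objection stands, so the finding rests on the time trigger.

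**Conclusion.** The point holds as an inconsistency between two stated treatment rules. It covers toxicity delays of 15 to 28 days past due (29 to 42 days since the last dose), apart from any patients whom the clinical-benefit agreement covers. It rests on counting the delay guidance from the due date, the only reading under which 1 or 2 weeks is a delay. The ±1 day visit window could blur the boundary between 14 and 15 days.

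The reach is narrow. Phase II gives no irinotecan, and phase I enrolls up to 12 patients. That is the number exposed to the rule, not the number expected to meet it; the documents do not say how often such delays occur.

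A reader might infer that the dose-finding result is at risk. The documents do not support that: the MTD decision rests mainly on toxicity in the first 28 days (Section 10.1), and the disputed days in the example begin at Day 44. What changes is irinotecan retreatment and exposure, and hence part of the triplet safety description.

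A reader might also see the same contradiction in Section 9.4, which says "If a treatment cycle is interrupted for more than 28 days, the decision to continue will be made by the investigator in agreement with" (sponsor-investigator named as the other party), and then "Continuous interruption of >28 days due to palliative radiotherapy will not be allowed". Those sentences can be read together as a general rule and a bar specific to radiotherapy, so they form no part of this finding.

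**What to change.** Reconcile the delay sentence in Section 10.4.1 with the stopping rule after Table 7, so that there is one maximum irinotecan interval counted from one named starting point (due date or last dose). In the same edit:

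- state whether a delayed dose counts as a missed scheduled dose;
- state whether the clinical-benefit agreement applies to the stopping rule or only to the diarrhea sentence;
- use the same starting point for the 28 days in the diarrhea sentence.

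The clinical team sets the limit; none is proposed here. The cost is a wording amendment, with no change to sample size, design or analysis.
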